6.2.1.1 Dosage, Administration, and Schedule

Blinatumomab will be administered as a continuous IV infusion.

Cycle 1 of blinatumomab treatment is 12 weeks (84 days) in duration and includes 8 weeks (56 days) of blinatumomab IV infusion followed by a 4-week (28-day) treatment-free interval.

The initial dose of blinatumomab will be 9 µg/day for the first 7 days of treatment. Blinatumomab dose will then be escalated (dose-step) to 28 µg/day starting on day 8 (week 2), followed by a dose-step up to 112 µg/day starting on day 15 (week 3) and continuing until completion of therapy (day 57 for cycle 1).

To evaluate disease status, MRD status (CT-DNA) will be assessed at cycle 1 day 1 prior to blinatumomab infusion, on cycle 1 days 15 and 43, the end of the blinatumomab infusion (day 57), and 2 weeks after the end of the blinatumomab infusion (day 71 + 3 days). A PET-CT will be performed only if subject remains MRD-positive at the day 57 assessment or has clinical signs and symptoms of disease progression.

Prior to initiation of blinatumomab and each dose-step escalation, dexamethasone will be administered as described in [Table 2](#).

The daily blinatumomab dose may be up to 10% lower or higher in order to account for possible pump inaccuracies. A dose of up to 10% higher than the intended dose may not require specific intervention. The effects of overdose of blinatumomab are not known. In case of overdose or medication error, the infusion should be immediately stopped. Consultation with the Amgen medical monitor is strongly recommended for prompt reporting of clinically apparent or laboratory adverse events possibly related to overdose. If the overdose results in an adverse event, the subject should be followed carefully until all signs of toxicity are resolved, and consultation with the Amgen medical

monitor is also strongly recommended even if there are no adverse events, in order to discuss the minimal duration of dose interruption. The adverse event(s) should be recorded/reported per [Section 9](#). Resumption of blinatumomab should adhere to the Dosage Adjustments, Delays, Rules for Withholding or Restarting, Permanent Discontinuation [Section 6.2.1.2](#).

The dosing, start and stop date and time, and lot number of blinatumomab is to be recorded on each subject's CRF.

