AE = adverse event; IV = intravenous; CT = computed tomography; CRP = C-reactive protein; ECG = electrocardiogram; ECOG PS = Eastern Cooperative Oncology Group performance status; HBsAg = hepatitis B surface antigen; HCVAb = hepatitis C virus antibody; HIV = human immunodeficiency virus; Ig = immunoglobulin; IP = investigational product; LDH = lactate dehydrogenase; MRD = minimal residual disease; PET = positron emission tomography; Q3 = every 3 months; EOS = end of study

^a Run-in period is up to 24 months in duration. During the run-in 1 period enrolled subjects that are MRD-negative/PET-CT negative will be followed at 3, 5, 7, 9 months and thereafter every 3 months (± 1 week) up to 24 months for MRD testing. At enrollment or during the run-in 1 subjects that are MRD-positive will complete Run-in 2 assessments to determine part 2 eligibility and treatment assignment.

^b **On days of hospitalization, obtain vital sign monitoring every 4 to 8 hours based on institutional standard of practice. When subject is in the outpatient clinic, only obtain 1 baseline vital sign per visit.**

^c Creatinine clearance is calculated by the Cockcroft-Gault equation

^d Pregnancy test must be performed within 72 hours from the start of run-in period and 72 hours prior to the first dose of blinatumomab (day [D] 1, cycle 1).

^e Lumbar puncture only required during treatment period if subject has a neurologic event leading to interruption/discontinuation or at seizure.

^f During the long term follow-up period an optional sample for MRD testing will be obtained at the time of suspicion of relapse and relapse.

^g PET-CT must be performed at run-in 2 in subjects that are MRD positive during run-in 1. Subjects that are MRD-positive at screening may qualify for treatment assignment with historical PET-CT negative results as long as PET-CT was performed ≤ 6 weeks from day 1 cycle 1 (first dose of blinatumomab) and subject has no clinical signs or symptoms suggestive of disease progression (eg, increase in LDH not otherwise explained). Every attempt should be made to complete PET and CT within 3 days of each other, particularly during blinatumomab treatment. PET-CT at day 71 (+ 3 days) will only be performed if subject remains MRD+ at cycle 1 day 57 or has clinical signs and symptoms of disease progression. During the long-term follow-up period a PET-CT or CT will be obtained at time of relapse and as per institutional standards for surveillance.

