7.2.6 Long-term Follow-up

Following the safety follow-up visit, there will be a long term follow-up period for clinical evaluation of disease status and survival. Subjects will be followed via clinical visit every 3 months (\pm 2 weeks) after their safety follow-up visit for a maximum of 1 year from the first dose of blinatumomab, or until subject death, whichever occurs first. During the long-term follow-up, subjects will be followed for MRD assessment and by institutional standard of care disease evaluation (PET-CT or CT) until relapse at which time the subject will be followed for survival via telephone contact.

Subjects will allow Amgen continued access to medical records so that information related to subjects' health condition, including disease status and survival, may be obtained.

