MRD status will be assessed at cycle 1 day 1 prior to blinatumomab infusion, on cycle 1 days 15 and 43, the end of the blinatumomab infusion (day 57) and 2 weeks after the end of the blinatumomab infusion (day 71 + 3 days) to evaluate disease status. A PET-CT will be performed only if a subject remains MRD-positive (day 57 of cycle 1 assessment) after blinatumomab or has clinical signs and symptoms of disease progression.

A safety follow-up visit will occur 30 days (+ 3 days) after the last dose of blinatumomab for assessment of disease-related events, adverse events, and serious adverse events. A long-term follow-up period to assess disease status and OS begins at completion of the safety follow-up visit and continues for 1 year from the first dose of blinatumomab. Subjects will be followed via clinic visit every 3 months (\pm 2 weeks) for MRD assessment and by institutional standard of care disease evaluation (PET-CT or CT) until relapse at which time the subject will be followed for survival via telephone contact.

A Data Review Team (DRT) will monitor the study for safety on a regular basis.

The overall study design is described by a study schema below.

Study Design and Treatment Schema

EOS = end of study; IP = investigational product;; MRD = minimal residual disease; PET-CT = positron emission tomography/computed tomography

^a Run-in period is up to 24 months in duration. During the run-in period, enrolled subjects that are MRD negative/PET-CT negative will be followed at 3, 5, 7 and 9 months and thereafter every 3 months up to 24 months for monitoring of MRD status by next generation sequencing.

^b At any time after enrollment and during the run-in period subjects who turn MRD positive/ PET-CT negative and that meet all other part 2 eligibility will be assigned to treatment with blinatumomab. Subjects that do not display MRD positivity at the end of the 24-month run-in period will end the study.

^c MRD status will be assessed at cycle 1 day 1 prior to blinatumomab infusion, on cycle 1 days 15 and 43, the end of the blinatumomab infusion (day 57), and 2 weeks after the end of the blinatumomab infusion (day 71 + 3 days).

^d Long-term follow-up period will be 1 year from the first dose of blinatumomab. Subjects will be followed via clinic visit every 3 months (± 2 weeks) until relapse and from this point onwards via telephone contact for overall survival.

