Duration of MRD-negative status will be defined from the time when a negative MRD result is first established until documented MRD-positive reoccurrence, or disease progression (or, death due to any cause). Subjects without any of these events at the time of the analysis will be censored at their last disease assessment date.

End of Treatment

End of Treatment is defined as the last assessment for the protocol-specified treatment phase of the study for an individual subject.

End of follow-up

End of Follow-up is defined as when the last subject completes the last protocol-specified assessment in the study.

End of study

For a subject: End of study for a subject is defined as the last day that protocol-specified procedures are conducted for an individual subject.

For the study as a whole: The end of trial is defined as the date when the last subject is assessed or receives an intervention for evaluation in the study (ie, last subject last visit), following any additional parts in the study (eg, long-term follow-up), as applicable.

The primary completion date: The primary completion date is defined as the date when the last subject is assessed or receives an intervention for the final collection of data for the primary endpoint, for the purposes of conducting the primary analysis, whether the study concluded as planned in the protocol or was terminated early.

High-risk first complete remission

High-risk first complete remission is defined as subjects who an interim PET-CT positive or less than complete remission to frontline chemotherapy AND achieved complete remission to platinum-containing salvage)

as collected on the Prior Anti-Cancer Therapies for Current Malignancies eCRF page.

International prognostic index (IPI)

International prognostic index (IPI) at diagnosis will be collected on the 'IPI at diagnosis' field on the DLBCL Disease History (Staging and Risk Initial) eCRF page. Secondary IPI at relapse will be collected on the 'IPI prior to S1' field on the DLBCL Disease History (Staging and Risk Prior S1) eCRF page.

Minimum residual disease (MRD)

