Minimum residual disease (MRD) is defined as negative when the tumor clone sequence in plasma is below the assay limit of detection (to be determined in the assay validation). Positive MRD status will be defined as plasma levels above the assay limit of detection. All subjects in the treatment period are considered MRD positive, regardless whether the Cycle 1 Day 1 MRD test results are positive or negative because these subjects have been tested MRD positive in the run-in period.

Overall survival (OS)

Overall survival will be defined from the first dose of blinatumomab treatment until death due to any cause. Subjects still alive at the time of the analysis will be censored at date last known to be alive.

Percent of intended dose of blinatumomab

For cycle 1, the percent of intended dose of blinatumomab will be the cumulative dose divided by the planned cumulative dose. The planned cumulative dose for cycle 1 will be $(9 \mu\text{g} \times 7 \text{ days}) + (28 \mu\text{g} \times 7 \text{ days}) + (112 \mu\text{g} \times 42 \text{ days}) = 4963 \mu\text{g}$.

Progression free survival (PFS)

Progression free survival (PFS) is calculated as the time from the date of first dose of blinatumomab until the date of diagnosis of relapse of lymphoma (by PET-CT, CT, clinical assessment or relapse biopsy, whichever is the preferred method), or date of death, whichever is the earliest. Subjects alive who did not have progression will be censored at last date of tumor assessment.

Refractory to frontline treatment

Refractory to frontline treatment is defined as failure to achieve complete response as the best response after completion of frontline chemotherapy, as collected on the Prior Anti-Cancer Therapies for Current Malignancies eCRF page.

Relapse within 1 year of diagnosis

A subject will be classified as relapsed within 1 year of diagnosis if the difference between the earliest date of relapse captured on the History of Relapses eCRF page and date of diagnosis on DLBCL Medical History eCRF page is less than 1 year.

Date of first relapse – Date of diagnosis + 1 < 365.25

Stage at diagnosis

As collected on the 'Ann-Arbor' field on the DLBCL Disease History (Staging and Risk Initial) eCRF page.

Study day 1

Study day 1 is defined as the first day that protocol-specified investigational products are administered to the subject.

Study day

Pre study day 1: study day= (date – date of Study Day 1)

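### Duration of MRD-negative status is censored at an undefined disease assessment date, so follow-up without an MRD sample can be counted as MRD-negative time

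*SAP*

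**What the plan says.** SAP section 5 (Definitions) measures the endpoint "from the time when a negative MRD result is first established until documented MRD-positive reoccurrence, or disease progression (or, death due to any cause"). It is therefore a composite of molecular recurrence, progression and death. Event-free subjects are handled by the sentence "Subjects without any of these events at the time of the analysis will be censored at their last disease assessment date." Protocol 10.4.3 has the same wording, so the two documents do not conflict on the rule.

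Neither document defines disease assessment. The PFS definition uses another undefined term: "Subjects alive who did not have progression will be censored at last date of tumor assessment." MRD negativity is defined (SAP section 5, Protocol 10.4.2) only as a tumor clone sequence in plasma below the assay's limit of detection.

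The documents give two accounts of MRD sampling in long-term follow-up:
- Protocol 7.2.6 says that "subjects will be followed for MRD assessment and by institutional standard of care disease evaluation (PET-CT or CT) until relapse", with visits every 3 months. SAP 3.1 agrees ("for MRD assessment and by institutional standard of care disease evaluation (PET-CT or CT) until relapse").
- Footnote f, the note attached to the follow-up MRD entry in Protocol Table 4, says: "During the long term follow-up period an optional sample for MRD testing will be obtained at the time of suspicion of relapse and relapse."

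No rule covers missed MRD samples for this endpoint. Protocol 10.1.4 and SAP section 5 address only whether negativity was achieved. SAP 8.3 refers missing-data rules to its sections 6 and 10, which are Analysis Sets and Changes From Protocol-specified Analyses.

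**The concern.** A scan or a node examination cannot show that a subject is still MRD-negative. The protocol's own argument (sections 2.2 and 2.4) is that plasma MRD turns positive before disease can be seen, with a cited median lead of 3.5 months in surveillance after frontline treatment. If the last disease assessment is later than the last MRD sample, the interval between them enters the Kaplan-Meier estimate as time at risk without an event, yet a molecular recurrence in it could not have been recorded. The estimated duration then leans in the drug's favour.

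Duration of MRD-negative status is a named secondary objective. It is estimated only in subjects who become MRD-negative, which is 0.30 × 30 = 9 subjects at the 30% rate of interest, so the handling of a few follow-up samples can shape the curve.

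**Working it through.** The plan states no figure for this endpoint, so there is nothing to reproduce. The check has two parts.

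**1. Schedule arithmetic**

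Inputs: infusion on days 1 to 56 (Table 4 footnote h); MRD samples on days 57 and 71; safety visit 30 days after the last dose (footnote i); follow-up every 3 months, about 91 days, for at most 1 year from first dose (footnote j).

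- Safety visit: 56 + 30 = day 86. Follow-up visits: 86 + 91 = 177, 177 + 91 = 268, 268 + 91 = 359.
- MRD sampled at every visit: last sample and last assessment share a date, so unmeasured time is 0 days.
- Final sample missed, visit attended: 359 − 268 = 91 unmeasured days.
- No sample after day 71: 359 − 71 = 288 days, or 365 − 71 = 294 if an assessment falls on day 365. A subject first negative on day 57 is credited with 359 − 57 = 302 days, of which 71 − 57 = 14 are supported by MRD data.

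**2. Effect on the Kaplan-Meier estimate**

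Assumptions, none given in the documents for this endpoint: first negative on day 57; exponential time to MRD recurrence, median 180 days; progression after a further exponential lag, median 105 days (3.5 months × 30); all clinic visits attended; no deaths or other dropout. A positive MRD sample counts as an event on its sample date.

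Reference with complete sampling: 0.5^(302/180) = 0.31 at 302 days.

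The case with no sample after day 71 has a closed form under the current rule. Let a = ln2/180 = 0.00385, b = ln2/105 = 0.00660, t = 302.
- Not progressed by t: (b·e^(−at) − a·e^(−bt))/(b − a) = (0.00660 × 0.3125 − 0.00385 × 0.1362)/0.00275 = 0.559.
- Subtract those already positive at the day 71 sample but not progressed by t: a·e^(−bt)·(e^(14(b−a)) − 1)/(b − a) = 0.007.
- Result: 0.559 − 0.007 = 0.55.

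The other entries are from simulation. Estimates at 302 days:

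| MRD sampling in follow-up | As written | Censor at last MRD sample; later progression still an event | Same cutoff for censoring and events |
|---|---|---|---|
| Every visit | 0.31 | 0.31 | 0.31 |
| Stops, 10% chance per visit | 0.36 | 0.28 to 0.29 | 0.30 |
| Stops, 30% chance per visit | 0.44 | 0.21 | 0.28 to 0.29 |
| None after day 71 | 0.55 | 0.00 | not usable after day 71 |

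Ranges are the spread over repeated runs. With isolated misses of 10% or 30% per visit, the current rule gives 0.32 or 0.35. With a 300-day median lag to progression, it gives 0.51 (30% stopping) and 0.75 (none after day 71).

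The third column shows that moving the censoring date alone overcorrects: subjects who progress later keep their event while event-free subjects are cut back to their last sample. Applying the cutoff to both removes most of the error. What remains is slightly downward, because a progression before the next due sample still counts.

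**The case against.** The strongest reply is that overstatement is conditional. Protocol 7.2.6 and SAP 3.1 have subjects followed 3-monthly for MRD, and Table 4 places clinical tumor assessment and MRD testing in the same follow-up column. If both are done at each visit, the two dates coincide and nothing is overstated. This stands. A reader might infer that the rule inflates duration in this trial; the documents show only that it can.

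Second, the term may be meant to include MRD. Protocol 6.2.1.1 says "To evaluate disease status, MRD status (CT-DNA) will be assessed at cycle 1 day 1", and PFS uses a narrower-sounding term. On an imaging-only reading the error could run the other way: SAP 3.1 says "A PET-CT will be performed only if a subject remains MRD-positive (day 57 of cycle 1 assessment") or has clinical signs, and follow-up imaging is left to institutional practice. A last scan could then precede the last MRD sample, and the rule would discard measured negative time. This also stands, and it is itself a reason to define the term.

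Third, the endpoint is a composite, so later clinical assessments do inform progression and death. That is correct, but they do not inform the molecular component, which on the protocol's rationale usually comes first.

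Fourth, it is tempting to say that every missed sample adds 91 days. Only a missed final sample moves the censoring date. A missed interior sample followed by a later negative one does not.

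**Conclusion.** The point holds in conditional form. The censoring date is undefined and not tied to an MRD measurement, and footnote f, read literally, allows disease assessments to continue without routine MRD samples. When that happens the bias is upward.

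The size depends on how many follow-up samples are missed, which the documents do not give. Under the stated assumptions the shift in the 302-day estimate is nil with complete sampling, +0.05 to +0.13 if sampling stops with 10% to 30% chance per visit (0.36 and 0.44 against 0.31), and +0.24 with no sample after day 71. A longer lag between MRD recurrence and progression makes it larger. A blanket statement that duration is overstated is not supported.

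The endpoint is secondary and summarised descriptively in a single-arm estimation study. Neither the primary MRD-negative rate nor N = 30 is affected. The change is worth making because it is cheap and the possible error favours the drug.

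**What to change.** Before the final analysis:

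1. In SAP section 5 and Protocol 10.4.3, replace the censoring sentence with a rule to this effect: *subjects without an event are censored at the date of their last evaluable negative MRD sample; in the main analysis, progression or death that follows one or more missed scheduled MRD samples is likewise censored at the last MRD sample.*
2. Keep the current rule, with all progressions and deaths as events, as a sensitivity analysis, and define disease assessment for it. This analysis matters because the main rule assumes that missed samples are unrelated to impending relapse.
3. Reconcile Table 4 footnote f with Protocol 7.2.6 and SAP 3.1 on whether follow-up visits include a routine MRD sample.

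The cost is a short text change and one derivation, with shorter follow-up, fewer events and wider intervals for this endpoint. If routine sampling stops, no usable estimate is available beyond the last MRD sample. That is a real loss, but it reflects what was measured.

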6.1 Full Analysis Set

The full analysis set will include all subjects who received blinatumomab. Subjects who were treated beyond the required sample size of 30 subjects will be included in this analysis set. The full analysis set will be used for the final analysis.

6.2 Primary Analysis Set

The primary analysis set will include the first 30 enrolled subjects who received at least 1 dose of blinatumomab. The primary analysis set will be used for the primary analysis.

6.3 Target Dose Analysis Set

The target dose analysis set will include all subjects from the full analysis set who completed at least 7 days of infusion on the highest intended dose. In addition, all subjects who discontinue treatment with blinatumomab due to disease progression during cycle 1 will also be included in the target analysis set. The target dose analysis set will be used as sensitivity analysis set for the final analysis.

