6.2.1.2.2 Infusion Interruptions/Dose Modifications Due to Adverse Events

Table 1. Infusion Interruptions/Dose Modifications Due to Adverse Events

Toxicity	Grade or Adverse Event	Instructions for Treatment Interruption and Restart
Cytokine Release Syndrome	3	
 Interrupt blinatumomab until the event improves to grade ≤ 1 and administer corticosteroids (refer to Table 2) Restart no less than 72 hours after the initial observation of the grade 3 event at the following dose levels: 
 If event occurred at 112 $\mu\text{g}/\text{day}$, resume at 28 $\mu\text{g}/\text{day}$ If event occurred at 9 or 28 $\mu\text{g}/\text{day}$, resume at 9 $\mu\text{g}/\text{day}$ Escalate up 1 dose level after 7 days if toxicity does not reoccur. Increase dose stepwise at 7-day intervals to target dose of 112 $\mu\text{g}/\text{day}$ if toxicity does not reoccur. Permanently discontinue if: 
 Initial grade 3 CRS does not improve to grade ≤ 1 within 7 days, OR Grade 3 CRS reoccurs at the lower dose level within 7 days of reinitiation OR Grade 3 CRS reoccurs at a dose of 9 $\mu\text{g}/\text{day}$ without prior dose-step escalation
	4	
 Permanently discontinue blinatumomab
Neurologic Events	3	
 Interrupt blinatumomab until the event improves to grade ≤ 1 and administer corticosteroids (refer to Table 2) Restart no less than 72 hours after the initial observation of the grade 3 event at the following dose levels: 
 If event occurred at 112 $\mu\text{g}/\text{day}$, resume at 28 $\mu\text{g}/\text{day}$ If event occurred at 28 $\mu\text{g}/\text{day}$, resume at 9 $\mu\text{g}/\text{day}$ Escalate up 1 dose level after 7 days if toxicity does not reoccur. Increase dose stepwise at 7-day intervals to target dose of 112 $\mu\text{g}/\text{day}$ if toxicity does not reoccur. Permanently discontinue if: 
 Initial grade 3 neurologic event occurred at 9 $\mu\text{g}/\text{day}$, OR Initial grade 3 neurologic event does not improve to grade ≤ 1 within 7 days, OR Grade 3 neurologic event reoccurs at the lower dose level within 7 days of re-initiation, OR Grade 3 neurologic event reoccurs at a dose of 9 $\mu\text{g}/\text{day}$
	4	
 Permanently discontinue blinatumomab

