9.5.2 Analyses of Secondary Efficacy Endpoint(s)

The secondary endpoints PFS, duration of MRD-negative status and OS will be summarized with Kaplan-Meier (KM) analyses on the Full Analysis Set for final analysis.

A sensitivity analysis will be performed on the Target Dose Analysis Set for final analysis.

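### The Target Dose Analysis Set selects on events after first dose, yet its PFS and OS analyses run from first dose with no landmark or delayed entry

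*SAP*

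**What the plan says.** SAP 6.3, which repeats Protocol 10.1.2.3, gives two ways into the Target Dose Analysis Set. The first is exposure: the subject "completed at least 7 days of infusion on the highest intended dose". The second is progression: "all subjects who discontinue treatment with blinatumomab due to disease progression during cycle 1 will also be included in the target analysis set". No dose or day is attached to the second route.

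Under SAP 9.5.2 and Table 9-2, the main analyses of the secondary endpoints "will be summarized with Kaplan-Meier (KM) analyses on the Full Analysis Set for final analysis". The section then adds: "A sensitivity analysis will be performed on the Target Dose Analysis Set for final analysis".

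SAP section 5 fixes the time origins. PFS is "calculated as the time from the date of first dose of blinatumomab until the date of diagnosis of relapse of lymphoma" or death, and for OS: "Overall survival will be defined from the first dose of blinatumomab treatment until death due to any cause". Nothing in SAP 5, 6.3, 9.5.2 or Table 9-2 changes the origin, or the time at which a subject comes under observation, when the Target Dose Analysis Set is used.

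Elsewhere the SAP does handle a status that becomes known only after treatment has started. SAP 9.5.3 compares PFS and OS by MRD status with a landmark at day 75, includes only subjects still in follow-up then, and counts time from day 75.

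**The concern.** Membership is decided after the clock has started, so the curves condition on what happened next. A subject who enters by exposure cannot have died in the first 21 days, yet those days count as survival time. Protocol 8.3.2 lists death and disease progression as separate reasons for leaving treatment, so an early death without progression fits neither route and disappears from the set. Of two subjects who stop on day 10, the one stopping for progression is in and the one stopping for toxicity is out. The second is not missing for lack of data: Protocol 6.2.1.3 keeps subjects who stop for adverse events in response assessment.

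What is at stake is how the two sets are compared. A difference between them would mix reaching the target dose with selection on early outcome. The components can also cancel, so agreement would be only weak reassurance.

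**Working it through.** **1. Day count.** SAP section 5 gives the planned cycle 1 dose, which confirms the schedule: 9×7 + 28×7 + 112×42 = 63 + 196 + 4704 = 4963 µg, as stated. The exposure route therefore needs 7 + 7 + 7 = 21 infusion days, complete at the end of day 21. This is a minimum. For grade 3 events Protocol Table 1 says "Restart no less than 72 hours after the initial observation of the grade 3 event at the following dose levels", with step-up at 7-day intervals, so the qualifying day varies between subjects.

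**2. Who is in the set**, by what happens before 7 days at the highest dose:

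| Event | In the set? |
|---|---|
| Stops for progression in cycle 1 | Yes |
| Dies, not recorded as progression | No |
| Stops for toxicity, later relapses or dies | No |
| Stops for toxicity, stays event-free | No |
| Stops at own request or for another reason | No |

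The documents give no rates for any of these rows. Every rate and count below is an assumption, apart from the planned 30 treated subjects.

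**3. Early deaths (OS).** With S of 30 alive at 12 months and d early non-progression deaths dropped, the set shows S/(30 − d).

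| S/30 | d = 1 | d = 2 | d = 3 |
|---|---|---|---|
| 15/30 = 50.0% | 51.7% | 53.6% | 55.6% |
| 21/30 = 70.0% | 72.4% | 75.0% | 77.8% |

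This component can only raise the estimate.

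**4. Toxicity stoppers (PFS).** Take 15/30 event-free and drop 3 early toxicity stoppers, k of whom have an event by 12 months. The set shows (12 + k)/27: 44.4%, 48.1%, 51.9% and 55.6% for k = 0, 1, 2 and 3. The sign depends on how these subjects fare.

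**5. Early progressors kept, toxicity stoppers dropped (PFS).** Take 15/30 event-free, 3 early progressors kept, and 6 toxicity stoppers dropped whose PFS equals that of everyone else who did not progress early (15/27 = 55.6%). The set holds 21 + 3 = 24 subjects and shows 21 × (15/27) / 24 = 48.6%, against 50.0% in the full set.

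**6. Simulation (PFS).** Constant hazard, 50% event-free at 12 months, 400,000 draws per scenario. Deaths without progression make up 5%, 20% or 50% of events. Toxicity stopping by day 21 is 0, 10% or 20%. Progression counts as the reason for stopping if it comes first and before day 56.

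- Exposure route alone: 51.9% to 52.1%, as expected from 0.5^(344/365) = 52.0%.
- Both routes as written, with toxicity stoppers at the same hazard as the rest: 49.8% to 51.0%, a shift of about 0 to +1 point.
- Both routes, with 10% or 20% stopping for toxicity at twice the hazard: full set 45.0% to 47.6%, target-dose set 49.6% to 50.9%. Paired differences run from +2.3 (47.6 to 49.9) to +5.8 (45.0 to 50.8). Most of this comes from removing the worse-faring stoppers, not from guaranteed time.
- Among subjects on drug and event-free at the start of day 22, counting 365 days from that point returns 49.9% to 50.1%, so resetting the clock removes the +2.

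**The case against.** The best defence is the progression route. A reader might infer that membership simply requires surviving and staying on drug to about day 22. The second sentence of SAP 6.3 rules that out: early progressors stay in, with their later deaths. This stands. It is why the simulated shift is 0 to +1 point and not +2 when toxicity stopping is uninformative. It does nothing for early deaths without progression or for early toxicity stops.

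Second, this is a descriptive sensitivity analysis of secondary endpoints in an estimation study with no formal test (SAP 2.2). The main PFS and OS analyses use every treated subject. Reasons for stopping are tabulated (SAP 9.2), as are adverse events leading to withdrawal and fatal events (SAP 9.6.2), so early toxicity stays visible. All of this stands and limits the severity, but those tables do not correct the curves.

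Third, the SAP nowhere says that the comparison measures an effect of reaching the target dose. That is true, but a sensitivity result set beside the main one will be compared with it, and the plan does not warn the reader.

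A reader might also infer that this is the only sensitivity analysis of PFS and OS. That holds for Table 9-2 only. Protocol 10.3.4 plans another, by MRD status, which SAP 9.5.3 carries out as an exploratory landmark analysis.

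**Conclusion.** The point holds, as a minor one. The set selects on events after first dose, its PFS and OS run from first dose, and nothing corrects for it. For OS, the omission of early non-progression deaths pushes the estimate up; the dropped live stoppers can add to this or offset it. For PFS the direction is not fixed. The shifts of about 0 to +1, about +2 to +6, and 48.6% against 50.0% rest on the assumed rates in steps 5 and 6. With 30 subjects, one subject is 3.3 points.

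Three stronger readings are not supported:

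- That the biases run in fixed, opposite directions for early death and early progression. Toxicity stoppers are excluded whether or not they later have an event, so the net sign for PFS depends on their outcomes.
- That agreement with the full set shows nothing. It is weak reassurance, which is a lesser charge.
- That the dropped early deaths are mostly caused by treatment. The documents hold no data on this.

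The Full Analysis Set results for PFS and OS are unaffected.

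**What to change.** In SAP 9.5.2 and Table 9-2, restrict the PFS and OS sensitivity analyses to subjects who reach 7 days at the highest dose, and choose one of two distinct methods:

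- **Delayed entry:** left-truncated Kaplan-Meier, keeping first dose as the origin, with each subject entering the risk set on his or her own qualifying day.
- **Landmark:** a single day stated in advance, with the clock reset there, as SAP 9.5.3 does at day 75.

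Require subjects to be alive at entry for OS, and alive and progression-free for PFS; OS does not need the second condition. Tabulate those who left before qualifying separately, by reason (death, progression, toxicity, other) and with their later outcomes. Label the analysis as conditional on post-baseline exposure.

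Keeping the set for MRD endpoints alone would not solve the problem. Protocol 10.1.4 counts subjects with missing post-baseline MRD as not negative, so dropping early stoppers without MRD results raises that rate too.

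The cost is SAP wording and minor programming. SAP section 10 now declares no changes from the protocol, so it should record this one. The revised analysis does not describe the first 3 weeks, and follow-up ends 1 year after first dose, so a day-22 landmark leaves about 365 − 21 = 344 days. The Full Analysis Set covers both gaps.
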